5.1 Derived Variables

5.1.1 Total Daily Dose

Total Daily Dose will be calculated as the sum of basal and bolus insulin dose per day from both diary data and CRF. The data from the two sources will be analyzed separately.

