10 Provide patient with required supply of BD Micro-Fine Plus 4 mm 32G needles (3 months' supply).			10 Collect the BGM from the patients. Complete the log forms
11 Schedule the HbA1c test and next personal visits in 90 and 180 days, and over-the-phone visits for interim control in 45 and 135 days.			
12 Provide patients the diary and a Blood Glucose Meter (BGM) with strips and lancets (3 months' supply). Explain how to complete the diary and use BGM.			
13 In a week +/-2 days after the screening visit, the investigator must ascertain if patient viewed recommended lessons.			

Visit № 1 – screening visit (personal visit).

1. For study purposes, prior to patient enrolment a physician will interview the patient about his/her condition in order to evaluate the effectiveness of current practices in terms of injection technique, the finding of gaps and possibilities for their improvement. Depending on the results of such an evaluation, the investigator will offer the patient familiarization with the corresponding distance learning modules.
2. Information about study participation is provided, and the informed consent form is signed.
3. Collection of the patient's demographic data and medical history data is carried out. The patient undergoes a physical examination to make sure that he/she meets the inclusion/exclusion criteria. A urine pregnancy test must be done for the childbearing potential female patients.
Examination of injection sites and injection technique is performed. The presence of lipohypertrophy is determined, and lipohypertrophy areas are marked on the diagram, indicating their number and size.
4. A physician makes an arrangement for the glycated hemoglobin test (HbA1c), which is carried out in the laboratory of the center participating in a given clinical trial at investigator's place of work.. To verify the inclusion criteria, the HbA1c value may be measured at screening or the latest measured value (max. 30 days prior to screening) may be taken. The result should be entered in the eCRF.
5. The current level of blood glucose and cases of hypoglycemia will be evaluated during the visit and the patient will be asked about his/ her condition and data will be completed in the eCRF.
6. The insulin dose of the day prior to the visit (basal and boluses) will be captured in the eCRF.

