13. Patients are instructed how to use the BGM and its accessories, how to complete the patient's diary. BGMs will be calibrated if needed and the date and time will be set correctly. Patients will be recommended to make at least 4 measurements of glucose per day by the provided BGM regardless of the type of diabetes: 3 before meals (one of which is before breakfast) and one measurement before bedtime. More measurements may be performed in accordance with clinical practice. The recommended measurements as listed above should be performed during the following time periods:

- a. within 2 weeks after screening,
- b. the last 2 weeks before the visit of the 3rd month, and
- c. the last 2 weeks before the visit of the 6th month.

The rest of the time, the patient may measure the level of glucose in the blood in accordance with accepted clinical practice.

During the same 2 weeks periods the patient is asked to complete the diary with basal and bolus insulin doses on a daily basis. Also, the patient has to complete the diary with all episodes of hypoglycemia.

14. The next meeting with the physician-investigator is scheduled in 90-100 days (visit № 3), as well as the interim visits, which include phone contacts in 45 +/-10 days (visit № 2) and in 135 +/-10 days (visit № 4).
15. A preliminary scheduled blood test for glycated hemoglobin takes place in 90 +/-10 days as well as in 180 +/- 10 days after the screening visit, to be carried out in the laboratory of the center participating in a given clinical trial at the investigator's place of work. The test must be done not sooner than a week before the study completion visit or on the day of the completion visit.
16. The Investigator informs the patient they have to visit the investigator before the next scheduled personal visit in case they do not have sufficient strips. Also, the patient can visit the investigator personally instead of the phone visit if the patient realizes they do not have enough strips to cover the period until the next scheduled personal visit. In this case, the patients have to bring the diary and his BGM for the visit and the Investigator will download the data from BGM and return it back to the patient. The diary will be kept by the investigator and the patient will receive the new diary. The patient also will receive the required number of strips in amount enough to the next scheduled personal visit.

1-week visit (optional, phone).

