2.5.2 Secondary Endpoints

- Change in total daily dose of insulin and clinical parameters of glycemic control (hypoglycemia and severe hypoglycemia requiring third party assistance) after 6 months follow up in patients with Type 1 or Type 2 diabetes.
- Change in glucose blood levels (measured by BGM) after 6 months follow up in patients with Type 1 or Type 2 diabetes.

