5.2.3 Total Daily Dose

For Total Daily Dose, analysis will be performed using linear mixed effect models to evaluate the effect of personalized teaching of the optimal insulin injection technique in conjunction with the use of disposable BD Micro-Fine Plus 32G pen needles on the response. In the model, subject will be a random effect, time period (baseline, 3 months or end of study), day in each time period, and lipohypertrophy will be fixed effects. Two-way and three-way interactions between fixed effects will be investigated. Only significant interactions will be included in the model. Models will be used to compute estimated mean, difference between baseline and end of study, and corresponding two-sided 95% CI for responses of interest.

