5.2.9 General Considerations

- Missing Insulin or Glycemic data might be imputed, as described in section 5.2.10.
- Imputation might be used during questionnaire analysis if questionnaire pre-process tools contain an imputation routine.
- p-values less than 0.05 will be considered statistically significant. Multiple comparisons adjustments will be made when adequate.
- For each model above, in case the model fails to converge for discrete responses, the random subject effect may be dropped from the model and the average difference between time periods may be calculated across all subjects.
- Initially, two-way interaction will be included into the model. However, if the interaction is not significant (p-value ≥ 0.05), it will be removed from the final model.
- Main effect and interaction plots may be used to graphically show significant effects for each model.
- Residual plots for each model will be drawn and reviewed to ensure there are no systematic patterns. Transformation of response and/or explanatory variables will be investigated whenever modelling assumptions are not satisfied.

- For analysis on discrete responses, a modeling approach will be attempted first and in cases where there are insufficient occurrences for model convergence or a stable model, difference in proportions between categories will be provided and non-parametric testing may be used if modeling assumptions, with or without data transformation, are not satisfied.

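### Insulin total daily dose is analysed from two sources with different baselines, and the SAP does not say which one decides

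*SAP*

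**What the plan says.** SAP 2.5.2 lists the endpoint once, without naming a source: "Change in total daily dose of insulin and clinical parameters of glycemic control", after 6 months of follow-up. SAP 5.1.1 then gives it two sources: "Total Daily Dose will be calculated as the sum of basal and bolus insulin dose per day from both diary data and CRF". It continues: "The data from the two sources will be analyzed separately".

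The protocol (7.5, Visit 1) defines what each source holds:

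- **CRF**, item 6: "The insulin dose of the day prior to the visit (basal and boluses) will be captured in the eCRF". Visits 3 and 5 record the day before the visit in the same way.
- **Diary**, item 13: "During the same 2 weeks periods the patient is asked to complete the diary with basal and bolus insulin doses on a daily basis". The three periods are the two weeks after screening and the last two weeks before the 3-month and 6-month visits.

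SAP 5.2.3 describes a single mixed model and does not say which source it covers. Subject is random, and "time period (baseline, 3 months or end of study), day in each time period, and lipohypertrophy will be fixed effects". SAP 5.2.10.2 admits insulin data only if at least ten days in each 14-day period have a record, and fills missing days with the subject's median for that period.

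On error control, SAP 5.2.9 says: "p-values less than 0.05 will be considered statistically significant. Multiple comparisons adjustments will be made when adequate". It gives no method and no family of tests. SAP 2.6 sets no acceptance criteria, and Protocol 10.2 names no source for TDD.

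**The concern.** A lower TDD is part of the trial's stated hypothesis (Protocol 6). With two analyses and no order between them, the plan does not say which one answers that part, or what is concluded if they disagree.

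The more serious problem is that disagreement need not be chance. Protocol 6 describes a before-and-after comparison, and training takes place at Visit 1. The CRF baseline lies before that training and the diary baseline lies after it. The protocol itself expects doses may move at this point. Under 7.6 the physician can recommend a lower TDD after Visit 1. Section 7.7 says patients who stop injecting into lipohypertrophic areas often need a reduction, sometimes of up to 20%. The diary contrast may therefore start from a dose that already contains part of the effect.

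A second test without a rule also raises the chance of a false finding for this endpoint.

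**Working it through.** **1. The plan's own figure.** The documents give no power, sample size or error rate for TDD. Their only such figure is for HbA1c: a decrease of 0.4, SD of paired differences 1.2, one-sample t-test, alpha 0.05, 80% power, N = 73. With the noncentral t distribution and two-sided alpha, power is 0.802 at N = 73 and 0.797 at N = 72, so 73 is reproduced. It does not depend on how TDD is handled.

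**2. What each source estimates.**

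| | CRF | Diary |
|---|---|---|
| Baseline | Day before Visit 1 (before training) | Two weeks after Visit 1 (after training) |
| End of study | Day before Visit 5 | Last two weeks before Visit 5 |
| Days per period | 1 | Up to 14 |
| Day-in-period term (SAP 5.2.3) | Cannot be estimated | Fits |
| Ten-of-14-days rule (SAP 5.2.10.2) | Can never be met | Fits |

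Let Δ be the full change from before training to month 6, and f the share of it already present, on average, in the baseline fortnight. The diary contrast is then (1 − f)Δ, while the CRF contrast is Δ. The documents give no value for f. At f = 0 the two agree; at f = 1 the diary shows no change.

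**3. Error rate if both are tested.** Inputs are two tests, each two-sided at 0.05 (SAP 5.2.3 and 5.2.9), with no true change. The test statistics Z₁ and Z₂ are taken as standard normal with correlation ρ. The documents do not give ρ, so a range is shown.

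- Any false significant result: 1 − P(|Z₁| < 1.96 and |Z₂| < 1.96). At ρ = 0 this is 1 − 0.95² = 0.0975.
- False reduction only: each test has a nominal 0.025 in that direction. The chance is 1 − P(neither test passes 1.96 in the direction of a reduction). At ρ = 0 this is 1 − 0.975² = 0.0494.

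| Assumed ρ | Any false result (nominal 0.05) | False reduction (nominal 0.025) |
|---|---|---|
| 0 | 0.0975 | 0.0494 |
| 0.5 | 0.0907 | 0.0454 |
| 0.8 | 0.0781 | 0.0390 |
| 0.9 | 0.0704 | 0.0352 |
| 0.95 | 0.0646 | 0.0323 |

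Relative to nominal, the inflation runs from 0.0975/0.05 = 1.95 times down to 0.0646/0.05 = 1.29 times. Both sources record the same patients' insulin, and at Visits 3 and 5 the CRF day falls inside the diary fortnight. The upper rows are therefore probably too pessimistic.

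**4. After the change.** With one deciding source the rates return to 0.05 and 0.025.

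**The case against.** The best defence is that the SAP never says the two analyses have equal standing. It says only that they are separate. The day term and the ten-of-14-days rule fit the diary alone, so one can fairly read SAP 5.2.3 as the diary model and the CRF dose as a secondary description. On that reading there is one formal test and no inflation. This carries weight, and it is why the error rates above are conditional on both sources being tested. It does not settle the matter: neither passage makes the diary deciding, and if the diary were deciding, the endpoint would rest on the source without a pre-training baseline.

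The SAP also provides for multiplicity adjustment. That provision has to be read with the 0.05 threshold, but it names no method, trigger or family and so commits to nothing for this pair.

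TDD is secondary, there are no acceptance criteria, and both analyses are stated in advance. No formal success decision turns on the choice. That limits the consequence but does not supply the missing rule.

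A reader might infer that the sponsor would choose the source after seeing the results. The documents give no evidence of such an intention; they only leave the choice open.

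**Conclusion.** The concern holds in a bounded form. One secondary endpoint has two separately analysed sources, no deciding one, and baselines on opposite sides of the training. The difference in baseline matters most, because it stands whatever is assumed about error rates. Its size depends on how fast doses change after Visit 1, which the documents do not give.

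If both sources are tested, the chance of any false significant TDD result is about 6.5% to 9.8% for correlations from 0.95 down to 0. This rests on an assumed correlation and a normal approximation.

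Two stronger readings are not supported. A reader might infer that the chance of falsely claiming a TDD reduction exceeds 5%. It does not: it is 3.2% to 4.9% over the same range, against a nominal 2.5%, because the larger figures also count false increases. A reader might also infer that the trial's main result is in doubt. The HbA1c analysis and the N of 73 are untouched.

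**What to change.** - **SAP 2.5.2, 5.1.1 and 5.2.3:** name the CRF TDD, day before Visit 1 against day before Visit 5, as the deciding secondary TDD analysis, because only it has a pre-training baseline. Fit it without the day-in-period term.
- **SAP 5.2.3 and 5.2.10.2:** state that the day term, the ten-of-14-days rule and the median imputation apply to diary data only. Otherwise the rule, read literally, would exclude every CRF dose from the deciding analysis.
- **Diary TDD:** report it as supportive, with estimate and 95% CI and no significance claim, and note that its baseline is after training.

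Splitting alpha at 0.025 per source would also control error (at most 4.94% for any false result), but would leave two different changes under one endpoint name.

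The change is to SAP wording and needs no new data or visits. Its cost is precision: a one-day dose is noisier than a 14-day mean, so the deciding interval may be wider. The documents give no TDD variances, so the amount cannot be computed.

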5.1.2 Hypoglycemia

The following categories will be analyzed:

- Hypoglycemia with blood glucose ≤ 3.9 mmol/L is defined as a blood glucose meter reading ≤ 3.9 mmol/L.

- Symptomatic Hypoglycemia with blood glucose ≤ 3.9 mmol/L is defined as a blood glucose meter reading ≤ 3.9 mmol/L. and occurrence of at least 1 symptoms of low blood sugar (e.g., fast heartbeat, tiredness, sweating, extreme hunger, dizziness, tremors) reported in the diary.
- Hypoglycemia with blood glucose ≤ 3 mmol/L is defined as a blood glucose meter reading ≤ 3 mmol/L.
- Symptomatic Hypoglycemia with blood glucose ≤ 3 mmol/L is defined as a blood glucose meter reading ≤ 3 mmol/L. and occurrence of at least 1 symptoms of low blood sugar (e.g., fast heartbeat, tiredness, sweating, extreme hunger, dizziness, tremors) reported in the diary.
- Severe hypoglycemia is defined as any event requiring third party assistance.

Events that are 15 min or closer to each other will be considered to be the same event. The lowest blood glucose value from the blood glucose meter will be used to define the Hypoglycaemia category.

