7. A theoretical course is given on lipohypertrophy and the necessity of alternating the injection sites, followed by hands-on classes on insulin injection technique. Also, patients are familiarized with other aspects of insulin therapy. Patients are given instructions that, in case of necessity, they can change the insulin dose during the clinical trial. The patient is not recommended to change the long-acting and intermediate-acting insulins, and not to change insulin subgroups, i.e., short-acting and ultra short-acting insulins.
8. The patient is familiarized with the structure and scope of the distance learning program. The whole course of video lessons will be recommended to the all patients for individual studies independently from their insulin injection technique success.
9. Patients are requested to complete the EQ-5D questionnaire, see Appendix B for an example.
10. Patients are supplied with an information package – booklet with instructions how to practice the right injection technique, rotation grid, the information letter for a physician in a local outpatient hospital to inform the patient is participating in the clinical trial. The letter should be formalized on the formal paper of the site. Guidelines on video lessons and web access codes, if required.
11. Patients will also receive:
 - a. disposable BD Micro-Fine 32G (0.23mm/32G x 4 mm) needles in the amount

required for 3 months (Table 3),

- b. Blood Glucose Meter (BGM), strips and lancets in the amount enough for 400 measurements, which corresponds with 100 days (approx. 3 months) of 4 measurements per day,
- c. a patient's diary. Patients are requested to record their insulin doses and if they experienced any adverse effects, including hypoglycemia's.

12. Patients must be informed to return the BGM back to the site after the study. Boxes of needles, boxes of strips and lancets will be marked: "BD property. Only for clinical trial. Not for sale". Glucometers will be marked: "BD property. Only for clinical trial. Not for sale. Must be returned".

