In 1 week +/- 2 days after the visit № 1, the investigator must be sure that the patient has viewed the recommended video lessons. To this end, the Sponsor provides the investigator with the report on the patient's use of the education resource. If the patient has not viewed recommended video lessons, then the investigator reminds him about the necessity of viewing the recommended video lessons. The information about video lesson viewing is marked in the patient's eCRF.

Visits № 2 and № 4- follow-up visits (over-the-phone visits, or personal visit).

1. The interim contacts with the patient are maintained over the phone in 45 +/-10 days and 135 +/-10 days from the first visit, with the view to evaluate the patient's adherence to the study design, review diary completion and to provide recommendations on the correction of the injection technique, as well as to evaluate the progress of his/her distance learning.
2. Information on the patient's glycemic control (glucose level), total daily insulin dose (the day prior to the phone visits) and hypoglycemic events since the last visit is requested and the information is entered in the eCRF.
3. To remind the patient to bring the BGM back on the next personal visit and to remind the patient on the appointment for having the HbA1c test, as was scheduled on the first and third visit
4. Data regarding possible AEs is collected in a special form of the patient's eCRF.
5. In case of the occurrence of adverse events (AE) in the course of the study after the screening visit, the investigator will record these in a special form (eCRF). In case of serious adverse events (SAE), the corresponding eCRF must be filled in and the event reported to the Sponsor and to the corresponding Ethics Committee within 2 working days after the investigator has become aware of the event.
6. The investigator has to remind the patient to measure their glucose levels upon the protocol requirements and complete the diary with insulin doses 2 weeks before the next personal visit. The same reminder will be also done 2 weeks before or even earlier the next personal visit.

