Quality of Life questionnaire (EQ-5D)	X			X
Patient examination for lipohypertrophy	X		X	X
Glycated hemoglobin (HbA1c)	X		X	X
Collect information on occurrences of hypoglycemia	X	X	X	X
Patient education classes, video lessons scheduling, provision of needles	X			
Control of video lessons' viewing	X	X	X	X
Exit from the study				X
Collection of adverse event information		X	X	X

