5.1.3 Blood Glucose

24 Hour Average Blood Glucose and other glycemic variability variables (such as MAGE, time in range, etc.) will be computed from BGM data using BD proprietary *extractGlucoseVariabilityFeatures()* and *summarizeGlycemicVariability()* functions with following arguments and associated computation per subject for different time ranges (e.g. day, study period, ...).

For BGM data, at least 10 days data for each period are needed for each time period for the analysis. The time window for baseline is defined as the first 14 days of the study. The time window for 3 month is defined as the last 14 days of the third month. The time window for end of study is defined as the last 14 days of the sixth month. The start and end of time window may be manually adjusted based on the actual visit time.

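### The four meter-based hypoglycemia categories have no pre-training period, and the hypoglycemia recorded at Visit 1 has no named analysis

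*SAP*

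**What the plan says.** Protocol section 6 describes the design as a before-and-after comparison. SAP 2.5.2 lists change in hypoglycemia after 6 months among the secondary endpoints.

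SAP 5.1.2 defines five categories. Four are non-severe and rest on a meter reading at or below 3.9 or 3 mmol/L; two of these also need a symptom noted in the diary. The rule for assigning events is: "The lowest blood glucose value from the blood glucose meter will be used to define the Hypoglycaemia category". The fifth category, severe hypoglycemia, depends on third-party help and not on a reading.

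For meter data, SAP 5.1.3 states: "The time window for baseline is defined as the first 14 days of the study". SAP 5.2.5 promises summary statistics for the five categories, a day/night split if data permit, and a distribution by study month.

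In Protocol 7.5, Visit 1 contains the training (item 7, a theoretical course "followed by hands-on classes on insulin injection technique"). It also contains the hand-out of supplies (item 11: new needles, a diary, and "Blood Glucose Meter (BGM), strips and lancets in the amount enough for 400 measurements"). The first recommended measuring period is "within 2 weeks after screening" (item 13).

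The protocol also records hypoglycemia at Visit 1 by asking the patient: "The current level of blood glucose and cases of hypoglycemia will be evaluated during the visit" (item 5), with the answer entered in the eCRF. The calendar of events (Table 2) has a row, "Collect information on occurrences of hypoglycemia", that is marked at every visit, including Visit 1.

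**The concern.** A before-and-after endpoint needs an observation from before the intervention. For the four non-severe categories, every source the SAP uses starts at Visit 1, where the intervention also starts. The period that SAP 5.1.3 calls baseline is therefore an early follow-up period. Meanwhile, the one hypoglycemia record that does look back before training, the Visit 1 eCRF entry, is not named in SAP 5.1.2 or 5.2.5.

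What is at stake is interpretation. A table that sets 'baseline' beside end of study will be read as the effect of training on hypoglycemia, when it shows early against late after training. A temporary change in the first two weeks would distort that reading, and a benefit that sets in at once and lasts would not show.

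**Working it through.** The documents give no hypoglycemia rate and no sample-size figure for this endpoint, so there is no plan figure to reproduce. The 73 evaluable patients relate to HbA1c and are not in question. The check is a trace of source and timing, followed by an illustration.

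**1. Where can a qualifying reading come from?** SAP 5.1.2 requires a meter reading. Protocol 7.5 (Table 1 and Visits 1 to 5) describes downloads from the supplied meter only. Readings from a patient's own earlier meter are not collected as data. The diary needed for the two symptomatic categories is also first issued at Visit 1.

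**2. When does that source start?**

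| Visit 1 step | Table 1 | Item list in 7.5 |
|---|---|---|
| Hypoglycemia asked about | 6 | 5 |
| Training | 7 | 7 |
| Meter and diary given out | 12 | 11 |

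Both lists put the hypoglycemia question before the training and the meter after it. The scheduled measuring period also follows screening. Days of meter data before training: 0.

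**3. Does any SAP time split reach further back?** The 14-day window in SAP 5.1.3 does not. Study month in SAP 5.2.5 does not. SAP 5.1.3 allows windows to be adjusted by hand to actual visit times, but there are no earlier meter data to move into.

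**4. How much of the intervention precedes the window?** The in-person training and the new needles precede all of it. The video lessons do not. At 1 week ± 2 days, "the investigator must be sure that the patient has viewed the recommended video lessons", so the check falls on day 5 to 9. Days of the window left after the check: 14 − 9 = 5 (5/14 = 36%) to 14 − 5 = 9 (9/14 = 64%). The window is thus after the in-person part and overlaps the distance-learning part.

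**5. Is the Visit 1 entry used?** SAP 5.2.5 is limited to the five categories. SAP 5.2.1 (all endpoints) and 6.3 (baseline variables) are general and do not name the entry. The sentence on further CRF information in SAP 5.2.6 concerns injection technique. By contrast, SAP 5.1.1 names both diary and CRF for total daily dose and analyses them separately. The CRF dose at Visit 1 is from the day before, so dose has a pre-training value with a named analysis and non-severe hypoglycemia has none.

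**6. Illustration only; none of these rates is in the documents.** Set the pre-training rate to 1, the weeks 1-2 rate to k and the end-of-study rate to e. Comparing the two meter periods gives e/k; the before-and-after ratio is e.

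- No lasting effect (e = 1): k = 0.8 gives 1/0.8 = 1.25 (+25%); k = 1 gives 1.00 (0%); k = 1.25 gives 0.80 (−20%); k = 1.5 gives 0.667 (−33%).
- Lasting effect e = 0.70, with a fraction f of it already present in weeks 1-2, so k = 1 − f(1 − 0.70): f = 0 gives 0.70; f = 0.25 gives 0.70/0.925 = 0.757; f = 0.5 gives 0.70/0.85 = 0.824; f = 0.75 gives 0.70/0.775 = 0.903; f = 1 gives 1.00.

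The apparent change can lie on either side of the true one.

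**The case against.** The strongest reply is that the SAP never commits to the contrast being criticised. SAP 5.2.5 specifies no model, test or baseline-to-end difference for hypoglycemia, and neither 5.1.2 nor 5.2.5 itself adopts the 14-day window. This stands. A reader might infer that the plan will report a biased training effect on hypoglycemia, perhaps from the appendix tables that compare time points. Those tables are marked as examples from previous studies, so the documents do not support that reading. What remains is an endpoint worded as a change, with only post-training meter data behind it.

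A reader might also infer a rise in hypoglycemia in the first two weeks, because Protocol 7.7 says patients who leave lipohypertrophic areas often need less insulin, sometimes by up to 20%. That passage is about lowering the dose to avoid hypoglycemia, and Protocol 7.6 lets the physician recommend a lower dose after Visit 1. Both work against an early rise, so the direction is not established.

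Two more points are fair. SAP 5.1.2 does not say the meter must be the study meter; that follows from what is downloaded. A descriptive table of the Visit 1 entry would fit within the general lines of SAP 5.2.1 and 6.3, but those lines do not direct the analyst to it.

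Finally, the missing pre-training readings come from the protocol design and the SAP cannot recover them. That is correct, and it is a reason to state the limit plainly.

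**Conclusion.** The point holds as a matter of labelling and of unused data. No meter-based period shows non-severe hypoglycemia before training: 0 days of pre-training coverage, assuming that Visit 1 follows its listed order and that only study-meter readings are analysed. The consequence is possible misreading of a descriptive secondary endpoint. The size and direction of any bias are unknown, and the ratios above show only that either direction is possible.

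Severe hypoglycemia is outside this point because its definition needs no meter. The primary HbA1c analysis is not affected, since its baseline is measured at screening or up to 30 days earlier. Priority: minor to moderate.

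**What to change.** 1. In SAP 5.1.2 and 5.2.5, label the first meter period 'weeks 1-2 after training'. State that meter-based differences from it are early versus late after training, not before versus after.
2. As SAP 5.1.1 does for total daily dose, summarise the eCRF hypoglycemia entries by visit as a separate source, with Visit 1 marked as before training. Title it 'hypoglycemia as recorded in the eCRF'. The title should not say whether events were meter-confirmed: the protocol's list of terms requires a confirmed reading, patients already self-monitor at entry, and the documents do not say how Visit 1 cases were verified. Give the recall period for each visit where known. Protocol 7.5 asks about events since the previous visit at Visits 2, 3 and 4, and states no period at Visits 1 and 5. Keep the table descriptive, because no Visit 1 recall period is stated.
3. State that change in non-severe hypoglycemia from before training cannot be estimated from the meter data.

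The cost is a wording change and one table from data already collected. The downside is that the meter data can no longer be presented as a before-and-after effect, and the Visit 1 entry, obtained by asking the patient, supports description only.
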